9.3 Characteristics of an Adverse Event

9.3.1 *Relationship to Study Intervention*

To assess relationship of an event to study intervention, the following guidelines are used:

1. Related (Possible, Probable, Definite)
 - a. The event is known to occur with the study intervention.
 - b. There is a temporal relationship between the intervention and event onset.
 - c. The event abates when the intervention is discontinued.
 - d. The event reappears upon a re-challenge with the intervention.
2. Not Related (Unlikely, Not Related)
 - a. There is no temporal relationship between the intervention and event onset.
 - b. An alternate etiology has been established.

9.3.2 Expectedness of SAEs

AMGEN and the Study PI will be responsible for determining whether an AE/SAE is expected or unexpected.

The most common adverse reactions (incidence $\geq 3\%$ and more often than placebo) in the migraine studies were injection site reactions and constipation. Common side effects that may affect between 1 and 10 people in every 100:

- Injection site reactions: which may include tenderness, pain, redness, itching, bruising, firmness, or hypersensitivity
- Constipation
- Muscle spasms/cramps
- Itching (pruritus)

Since erenumab was approved in May 2018, the following events have been reported in patient's exposed to erenumab in the post-marketing setting:

- 1) Severe allergic reactions such as rash, swelling and difficulty breathing, or swallowing.
- 2) Mouth/lip sores (e.g., stomatitis, mouth ulcerations, and oral mucosal blistering)
- 3) Skin and subcutaneous tissue disorders
 - o Alopecia (loss of hair)
 - o Rash (e.g., papular rash [small raised red rash], exfoliative rash [redness and/or peeling of skin], erythematous rash [red rash], urticaria [hives], and blisters)
- 4) Constipation and the use of medications that decrease gastric motility are in our exclusion criteria, however if a new onset of constipation occurs, the participant will be withdrawn of the study and will be referred to an appropriate practitioner for continued care (see section 9.2).
- 5) Hypertension or worsening of high blood pressure can happen after receiving Erenumab. Hypertension is in our exclusion criteria, however if a new onset of hypertension occurs, the participant will be withdrawn of the study and will be referred to an appropriate practitioner for continued care (see section 9.2)

An adverse event (AE) will be considered unexpected if the nature, severity, or frequency of the event is not consistent with the risk information previously described for the intervention, protocol, investigator's brochure and/or informed consent document.

9.3.3 Severity of Event

Severity grades will be based on the Common Terminology Criteria for Adverse Events (CTCAE)

grade 1 = mild; grade 2 = moderate; grade 3 = severe or medically significant; grade 4 = life-threatening consequences; and grade 5 = death.

9.4 Reporting Procedures

9.4.1 *Unanticipated Problem Reporting to IRB and AMGEN*

Incidents or events that meet the OHRP criteria for unanticipated problems require the creation and completion of an unanticipated problem report form within the Electronic Data Capture (EDC) system. Following OHRP recommendations the investigators will include the following information when reporting an adverse event, or any other incident, experience, or outcome as an unanticipated problem to the IRB and AMGEN Safety:

- Appropriate identifying information for the research protocol, such as the title, investigator's name, and the IRB project number.
- A detailed description of the adverse event, incident, experience, or outcome.
- An explanation of the basis for determining that the adverse event, incident, experience, or outcome represents an unanticipated problem.
- A description of any changes to the protocol or other corrective actions that have been taken or are proposed in response to the unanticipated problem.

[REDACTED]

[REDACTED]

[REDACTED]

[REDACTED]

- All unanticipated problems will be reported to appropriate institutional officials (as required by an institution's written reporting procedures), the supporting agency head (or designee), and OHRP within one month of the IRB's receipt of the report of the problem from the investigator.

All unanticipated problems will be reported to AMGEN Safety via email by the investigator. These reports will be reviewed by the IRB.

[REDACTED]

[REDACTED]

[REDACTED]

[REDACTED]

9.4.2 *Serious Adverse Event Reporting to AMGEN Safety and UMB IRB*

[REDACTED]	[REDACTED]	[REDACTED]
[REDACTED]	[REDACTED]	[REDACTED]
[REDACTED]	[REDACTED]	[REDACTED]

[REDACTED]

[REDACTED]

Any AE meeting the specified Serious Adverse Event criteria will be submitted on an SAE form to the IRB and AMGEN Safety. [REDACTED]

[REDACTED]

[REDACTED]

[figure not shown]
[figure not shown]
[figure not shown]
[figure not shown]
[figure not shown]
[figure not shown]
[REDACTED]

[REDACTED]

[REDACTED]

[REDACTED]

[REDACTED]

10. **What is the primary purpose of the *Journal of Clinical Endocrinology and Metabolism*?**

1. **What is the primary purpose of the study?** The study aims to evaluate the effectiveness of a new treatment for hypertension in a diverse population.

Black box

100% of the time, the *hedgehog* is a hedgehog, and the *cat* is a cat.

11. **What is the primary purpose of the study?** (check all that apply)

The PI will complete a Serious Adverse Event Form and submit via fax or email within the following timelines:

- All deaths and immediately life-threatening events, whether related or unrelated, will be recorded on the Serious Adverse Event Form and submitted to Product Safety within 24 hours of site awareness.
- Serious adverse events other than death and immediately life-threatening events, regardless of relationship, will be reported by fax within 72 hours of site awareness.

All SAEs will be followed until resolution or stabilization.

9.4.3 *Reporting of SAEs and AEs to FDA*

FDA reporting is not applicable.

9.4.4 *Events of Special Interest (if applicable)*

Any clinically significant finding of worsening of a medical condition other than TMD established at baseline/Visit 0 or the development of any new clinically significant medical condition throughout the study will be considered an AE and will be reported as described previously.

9.4.5 *Reporting of Pregnancy*

Pregnancy will be considered a SAE. If a participant becomes pregnant at any time during the study, it will be recorded on a case report form within the EDC system. Pregnancy/lactation exposure and any associated reports/outcomes (i.e. unexpected pregnancy, pregnancy of partner, spontaneous abortion, congenital anomaly etc.) will be reported within 1 business day of sponsor/PI awareness, for reports meeting serious criteria and not to exceed 15 calendar days of sponsor awareness, for non-serious reports to IRB and AMGEN Safety (As mentioned on 9.4.2 Table 2).

Participants who become pregnant while participating in the study will be withdrawn from the study and referred for appropriate care. If a participant becomes pregnant while receiving the study drug, she will be followed for safety until a pregnancy outcome is reached. If the pregnancy results in an outcome other than a normal birth or elective abortion of a healthy fetus, it will be reported as an SAE.

9.5 Halting Rules

This is addressed in Section 5.6. Based on the findings of a (scheduled or ad-hoc) safety review, the study may be temporarily suspended to enrollment (or to an

intervention), or it may be prematurely terminated.

Depending on the findings of a safety review, the medical monitor, UMB (sponsor) IRB, or the DSMB will determine whether the study: should continue per protocol; proceed with caution; be further investigated; be modified; or be terminated.

Some types of events that might trigger a safety review are: number of SAEs overall; prevalence of a specific SAE; number/type of severe AEs; or increased frequency of AEs.

10 STUDY OVERSIGHT

In addition to the PI's responsibility for oversight, study oversight will be under the direction of a Data and Safety Monitoring Board (DSMB) composed of members with expertise in pain management and TMD management at the sponsor site. The PI and DSMB will meet on a predetermined schedule to assess safety and efficacy data, study progress, and data integrity for the study.

11 CLINICAL SITE MONITORING

Clinical site monitoring is conducted to ensure that the rights of human subjects are protected, that the study is implemented in accordance with the protocol and/or other operating procedures, and that the quality and integrity of study data and data collection methods are maintained. Monitoring for this study will be performed by the IRB UMB. The monitor will evaluate study processes and documentation based on IRB UMB standards and the International Conference on Harmonisation (ICH), E6: Good Clinical Practice guidelines (GCP).

12 STATISTICAL CONSIDERATIONS

12.1 Study Hypotheses

The main objective of the statistical analysis is to estimate change in study endpoints and evaluate the efficacy of Erenumab by testing a priori hypothesis concerning the differences between treatment and placebo.

Erenumab reduces pain and restores function in patients suffering of TMD.

The primary efficacy hypothesis is that Erenumab produces greater change in average pain score (0-100 scale) from Visit 1 to Visit 4 than placebo.

The secondary efficacy hypothesis is that Erenumab produces a greater proportion of patients reaching at least a 50% reduction from baseline in monthly TMD pain days compared to placebo. This will be determined as a change from baseline phase (4 weeks) through the 12 weeks treatment phase (3 cycles) until Visit 4.

Functional measures related to TMJ biomechanics and pain related behaviors:

There is a greater proportion of patients achieving $\geq 30\%$ decrease (score) in limitation of jaw function with the use of erenumab after 12 weeks of treatment compared to placebo.

There is a greater proportion of patients achieving $\geq 30\%$ decrease (score) in oral behaviors with the use of erenumab after 12 weeks of treatment compared to placebo.

There is a greater proportion of patients achieving $\geq 30\%$ increase in value in pressure pain thresholds in temporalis, masseter, trapezius muscles, TMJs and epicondyles with the use of erenumab after 12 weeks of treatment compared to placebo.

There is a greater proportion of patients achieving $\geq 30\%$ decrease in intensity and pain related disability (GCPS) with the use of erenumab after 12 weeks of treatment compared to placebo.

There is a greater proportion of patients achieving $\geq 30\%$ increase in score (impression of improvement/ impression of change/PGIC) with the use of erenumab after 12 weeks of treatment compared to placebo.

There is a greater proportion of patients achieving $\geq 30\%$ decrease (score) in anxiety and depression (change in HADS) with the use of erenumab after 12 Weeks of treatment compared to placebo.

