5.4 Treatment Assignment Procedures

This will be a conventional factorial design, randomized, double-blinded clinical trial with two parallel arms to evaluate efficacy of Erenumab:

- Erenumab, a monoclonal antibody medication that inhibits the CGRP pathway, which is FDA-approved for the prevention of migraine in adults. The comparison will be to placebo.

5.4.1 *Randomization Procedures (if applicable)*

Extensive screening procedures of potential participants to determine their eligibility based on the inclusion and exclusion criteria will be carried out prior randomization. Participants who do not meet these criteria will not be enrolled in the study.

Randomization visit will be within 7 days after Visit 0, eligibility will be further confirmed based on completion of Daily Symptom Diaries and pain intensity score. Qualified participants will be randomly assigned to one of the two arms of the study in a 1:1 ratio:

- 1) Investigational arm: Erenumab: N= 30 participants
- 2) Placebo: N=30 participants

Randomization

Subjects will be randomized to the investigational treatment group (Erenumab) or the placebo group using a blocked randomization scheme. The examiners and patients will be blind to the group assignment. Randomization will be done by Investigational Drug Services (IDS/Research pharmacy). There will be a 1:1 ratio of treatment to placebo participants.

Blinding

Blinding will be done by Investigational Drug Services (IDS). The PI and study staff will be blind to what the participant is receiving.

Treatment/randomization codes

IDS will be responsible for randomization of participant assignment to either the study medication or placebo groups. IDS will use a random number generation program to determine assignment.

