12.2 Sample Size Considerations

The proposed sample size of 60 randomized patients split into two independent groups is based on a 30-50% reduction in TMD pain scores at follow-up, assuming a power of 90%, alpha = 0.05, assuming a 0.5 (medium) effect size. This was calculated using GPower software. This sample size is also based on the conservative assumption of a 15% patient drop out at follow up.

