12.4 Final Analysis Plan

The main goal of the statistical analyses is to estimate change in study primary and secondary endpoints to evaluate efficacy of Erenumab. Intention to treat analysis will be performed using a within-subjects student's pair t-test or repeated measures ANOVA (if more than two time points) to determine significant reduction in pain after drug intervention in each patient. Subsequently, a between-subjects unpaired t-test or two-way mixed designed ANOVA (if more than two time points) will be performed to determine difference between the placebo and erenumab groups. *Post-hoc analysis* will only be conducted following a significant ANOVA test, to protect from Type I errors. We will use a 2-way between subject's repeated measure ANOVA design to determine difference between the Erenumab group and placebo group, or a between-subjects unpaired t-test if two groups only. We will also use student's paired t-test to determine time points of significance. 50% reduction in pain days will be determined as a function of baseline pain days. Where, appropriate similar statistical procedures will be used for secondary endpoints.

Descriptive statistics for safety measures will also be calculated.

We will collect the following data for descriptive purposes and, if necessary, to use as covariates: Demographic information (age and race/ethnicity), rescue medication history, psychological factors and perceived change in overall status (PGIC).

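### Section 12.1 states seven secondary efficacy hypotheses (7 to about 13 tests) with no alpha, gate or adjustment across endpoints

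*Combined protocol and SAP*

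**What the plan says.** Section 12.1 says efficacy will be judged by testing hypotheses fixed in advance. After the primary it states "The secondary efficacy hypothesis is that Erenumab produces a greater proportion of patients reaching at least a 50% reduction" in pain days. Under functional measures and pain-related behaviours it then adds six further hypotheses, each that more patients on erenumab than on placebo reach a 30% change: jaw function, oral behaviours, "pressure pain thresholds in temporalis, masseter, trapezius muscles, TMJs and epicondyles", GCPS intensity and disability, PGIC, and HADS anxiety and depression.

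Section 3.1 frames all of these as questions of efficacy, and lists pain days first and separately.

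Section 12.4 gives the secondary analysis one sentence: "Where, appropriate similar statistical procedures will be used for secondary endpoints". Its only Type I safeguard is that post-hoc comparisons are made only after a significant ANOVA. An alpha appears only in the sample-size paragraph, Section 12.2: "assuming a power of 90%, alpha = 0.05, assuming a 0.5 (medium) effect size". No section states an alpha or sidedness for the secondary tests, a condition that the primary must succeed first, or an adjustment across endpoints.

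**The concern.** The post-hoc rule in 12.4 limits follow-up comparisons within a single ANOVA. It does not limit how many separate endpoints can each yield a claim, and the hypotheses in 12.1 concern responder proportions on different instruments.

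As written, one nominally significant secondary p-value could be reported as an erenumab effect even if the primary test were negative. It could come from a site remote from the jaw, such as the epicondyles. A reader would have no stated rule for telling a confirmatory result from a chance one. A negative primary is a realistic outcome (see the power figures in the working), so this is when the gap would matter.

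**Working it through.** **Plan's own figure.** The documents give no family-wise error rate, so there is none to reproduce.

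**Number of tests.** In the order pain days, jaw function, oral behaviours, PPT, GCPS, PGIC, HADS:
- One test per hypothesis: 1+1+1+1+1+1+1 = 7.
- PPT split by site: 1+1+1+5+1+1+1 = 11. Section 8.1 supports this, because it records one PPT value per anatomical site and 12.1 names five sites.
- GCPS (two dimensions, Section 8.1) and HADS (anxiety, depression) split as well: 1+1+1+5+2+1+2 = 13. Section 12.1 names the components but does not say they are tested separately.

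**Assumptions.** Two-sided 0.05 per test, carried over from 12.2; no drug effect on any endpoint; correlation between endpoints not given, so a common value is varied.

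**Independent tests.** Chance of at least one false finding = 1 − (1 − α)^k.
- Either direction, α = 0.05: 1 − 0.95^7 = 30.2%; 1 − 0.95^11 = 43.1%; 1 − 0.95^13 = 48.7%.
- Favouring erenumab only, α = 0.025: 1 − 0.975^7 = 16.2%; 1 − 0.975^13 = 28.1%.

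**Correlated tests.** Simulation of equicorrelated normal test statistics, 200,000 replicates:

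| Correlation | 7 tests, either direction | 13 tests, either direction | 7 tests, favourable | 13 tests, favourable |
|---|---|---|---|---|
| 0.3 | 27.1% | 41.9% | 13.8% | 21.3% |
| 0.5 | 22.8% | 33.4% | 11.4% | 16.8% |
| 0.7 | 17.6% | 24.0% | 8.8% | 12.0% |
| 0.9 | 11.4% | 13.7% | 5.8% | 6.8% |

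The single-test benchmarks are 5% in either direction and 2.5% favourable.

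**Effect of the test chosen for proportions.** The plan names none. At 30 per arm and a common response rate of 10% to 50%:
- Fisher's exact test has a true two-sided size of 0.9% to 2.7%. Under independence this gives 6% to 18% (7 tests) or 12% to 30% (13 tests) in either direction, and 3% to 9% or 6% to 16% favourable.
- The uncorrected chi-square test has a true size of about 4.9% to 5.4%, so the nominal figures stand almost unchanged.

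**Power of the primary, which sets the cost of a gate.** Taking 12.2 as an unpaired two-sided comparison with d = 0.5:
- Normal approximation, 30 per arm: 0.5 × √(30/2) = 1.936; 1.936 − 1.960 = −0.024; power 49%. The noncentral t gives 48%.
- After 15% dropout, 30 × 0.85 = 25.5 per arm: 0.5 × √(25.5/2) = 1.785; 1.785 − 1.960 = −0.175; power 43%. The noncentral t gives 42%.

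On this reading the stated 90% does not reproduce; it needs 86 per arm before dropout. A repeated-measures interaction (f = 0.25) reaches about 60 only with a correlation that the plan does not state: about 0.42 to 0.45 with two time points, or 0.3 with three. That is a separate matter and does not enter the error rates above.

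**The case against.** The case on the other side has real weight. This is a single-centre phase II trial of 60 patients, its secondary outcomes are described as exploring efficacy further, and 12.1 aims to estimate change as well as to test. Strict control over every secondary endpoint would be partly a matter of preference. The primary error rate is untouched.

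Four stronger readings are tempting, and the documents do not support them:

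- **That an inert drug has a 30% to 49% chance of a false secondary finding.** Those figures need independent tests. These are related pain, function and mood measures in the same patients, including five threshold sites, so positive correlation is likely. The hypotheses are also directional, and false claims of benefit are about half as frequent under two-sided testing. One-sided 0.05 tests would bring the benefit figure back to 30% to 49%, again only under independence.
- **That every test will be run at full alpha.** The 0.05 is stated for sample size only, and 12.4 qualifies its secondary analyses as applying where appropriate.
- **That there are at least 13 tests.** The PPT split is well supported; the GCPS and HADS splits are plausible but unstated. Seven is a fair reading.
- **That nothing is ranked.** Pain days is plainly singled out in 12.1 and 3.1. What is missing is any consequence of that ranking.

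A separate Statistical Analysis Plan is listed among the supplemental materials and could contain a rule. It is described as outside the protocol and modifiable without amendment, and nothing in the reviewed text commits it to one.

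What survives is that 3.1 and 12.1 promise efficacy conclusions on these endpoints without saying which of them could be confirmatory.

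**Conclusion.** The concern holds as a gap in the plan. Seven secondary efficacy hypotheses, giving 7 to about 13 tests, have no stated alpha, gate or adjustment, and the lead given to pain days has no alpha consequence.

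If each is tested at two-sided 0.05, the chance of at least one false finding is about 30% to 49% under independence and about 18% to 42% at an assumed common correlation of 0.3 to 0.7. For false findings favouring erenumab it is about 16% to 28% and 9% to 21%. These are conditional figures. They rest on an assumed alpha, sidedness, correlation and test, and Fisher's exact test lowers them. In the most conservative case calculated (seven independent Fisher tests, 10% response rate, favourable direction only) the chance is about 3%, so not every scenario exceeds 5%. Most do.

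Severity is minor: the primary inference stands, but secondary results could not be read as confirmatory under the present text.

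**What to change.** In 12.4, name the pain-day responder comparison as the only formally tested secondary hypothesis, and state that it is interpreted as confirmatory only if the primary is significant at 0.05. Report all other secondary measures as between-group estimates with 95% confidence intervals, labelled descriptive, with no efficacy claim drawn from their p-values. This gives effect to the ranking already in 12.1 and holds the error rate for confirmatory claims at 5%.

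The cost is about two sentences, with no extra patients or data. The downside should be stated openly: fewer secondary results can be called confirmatory. On the unpaired reading of 12.2, with primary power of about 48% at 30 per arm and about 42% after dropout, the gate would stay closed about 52% to 58% of the time even if the assumed effect were real, and the pain-day result would then be descriptive too.

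Holm's procedure across the remaining measures after a successful pain-day test is possible, but it is a trade-off in a trial of this size. Descriptive labelling is the simpler choice.

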3.2.2 Secondary

Efficacy will be investigated further using secondary outcomes:

TMD pain days: Percentage of participants with at least a 50% reduction from baseline in monthly TMD pain days. Time Frame: Baseline phase, the 12 weeks of management and until Visit 4.

Definition of TMD pain day: A TMD pain day was any calendar day in which the participant experienced pain, stiffness, soreness, tenderness, in the jaw or temple area or either side being brief or continuous; and/or pain with TMJ biomechanics (chewing, mouth opening or any jaw movement; and/or pain with jaw activities (yawning, kissing, talking); and/or pain with jaw habits (chewing gum, clenching, grinding).

At least a 50% reduction from baseline in monthly TMD days will be determined if the change in monthly TMD days from baseline phase through the 12 weeks treatment phase (3 cycles) * 100 / baseline monthly TMD days less than or equal to -50%.

Functional measures related to TMJ biomechanics and pain related behaviors:

TMD examination and Jaw functional limitation Scale: Change related to TMJ biomechanics/Jaw function and symptomatology in response to TMD examination.

Oral Behaviors (OBC): Changes in parafunctional behaviors

Pressure Pain Thresholds: Changes in myalgia and arthralgia

Graded Chronic Pain Scale (GCPS): Changes in pain intensity and pain related disability

Patient Global Impression of Change (PGIC): Assesses patient perspective of pain improvement

Hospital Anxiety and Depression Scale: Evaluation of Anxiety and depression

Exploratory Endpoint

To investigate the efficacy of Erenumab in decreasing pro-inflammatory cytokine release

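### Five secondary measures are 30% responder proportions in 12.1 but changes in 3.2.2 and 12.4, so endpoint and test are not fixed; the responder route usually costs power

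*Combined protocol and SAP*

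**What the plan says.** Section 12.1 (Study Hypotheses) states each functional hypothesis as a greater proportion of patients on erenumab reaching a 30% or greater change. For jaw function this is a "decrease (score) in limitation of jaw function with the use of erenumab after 12 weeks of treatment compared to placebo". For the pain scale it is a "decrease in intensity and pain related disability (GCPS) with the use of erenumab after 12 weeks of treatment compared to placebo", and for mood a "decrease (score) in anxiety and depression (change in HADS) with the use of erenumab after 12 Weeks of treatment compared to placebo". Oral behaviours have the same form, and pressure pain thresholds (PPT) have it as a 30% or greater increase.

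Section 3.2.2 (Secondary) gives the same measures without a cut. Jaw function is "Change related to TMJ biomechanics/Jaw function and symptomatology in response to TMD examination". The pain scale reads "Graded Chronic Pain Scale (GCPS): Changes in pain intensity and pain related disability". Oral behaviours and PPT are also listed as changes, and HADS as an evaluation. The one responder endpoint that 3.2.2 does define, a 50% reduction in TMD pain days, comes with its own formula; these measures have none.

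Section 12.4 (Final Analysis Plan) sets the aim as estimating change. It names paired and unpaired t-tests and repeated-measures or mixed ANOVA, and applies similar procedures to secondary endpoints where appropriate. It names no test for proportions.

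The entry criteria in 5.1 require diary pain of at least 30, or pain of at least 30 on three or more days of the preceding week. They also require pain modified by jaw biomechanics and a DC/TMD myalgia finding. They set no minimum score on any of these measures, and no section has a rule for a zero baseline.

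**The concern.** Two analyses can each claim support from the text: a comparison of proportions (12.1) and a comparison of mean changes (3.2.2 with 12.4). They can give different answers in a trial of 60, and nothing says which one counts. The choice could be made after the data are seen.

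If the responder form is used, each score is reduced to yes or no, which discards information already collected. A percent-change rule also behaves badly at the bottom of a scale. A patient at zero has no percent change, and a patient near zero can cross 30% on a trivial difference. Such patients must be dropped or counted by a convention that the plan does not give.

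**Working it through.** **The plan's own figure.** Section 12.2 gives 60 patients for 90% power, alpha 0.05, effect size 0.5 and 15% dropout. It concerns pain scores; no figure is given for these measures. For two groups, n per arm ≈ 2(1.960 + 1.282)²/0.5² = 84.1, so 85, or 86 with the t distribution. That is 172 in total, or 172/0.85 = 203 with dropout. The stated 60 is not reproduced as a two-sided between-group comparison. At 30 per arm and d = 0.5 the power is 48%.

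**Inputs.** 30 per arm (12.2); 60 × 0.85 = 51 completers, so 26 v 25; two-sided alpha 0.05 (sidedness is not stated). Responder rates are not in the documents and are assumed.

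**Power under additive normal change, 40% v 20% responders.**
- Implied standardised difference: d = z(0.80) − z(0.60) = 0.842 − 0.253 = 0.588.
- Score: noncentrality = 0.588 × √(30/2) = 2.28; t-test power 61.0%.
- Proportions: the null SE is √(0.30 × 0.70 × 2/30) = 0.1183, so the expected z is 0.20/0.1183 = 1.69. With alternative SE √((0.24 + 0.16)/30) = 0.1155, power ≈ Φ((0.20 − 1.96 × 0.1183)/0.1155) = Φ(−0.28) ≈ 39%. Exact enumeration gives 39.2% for chi-square and 29.8% for Fisher.
- At 26 v 25: 53.9%, 35.4% and 27.0%.

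**Range at d = 0.5, 30 per arm.** The active rate is Φ(z(control) + 0.5).

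| Control | Active | Score | Two proportions | Fisher | n per arm to match score |
|---|---|---|---|---|---|
| 20% | 36.6% | 47.8% | 29.5% | 21.2% | 54 |
| 30% | 49.0% | 47.8% | 32.2% | 23.5% | 48 |
| 40% | 59.7% | 47.8% | 33.0% | 25.1% | 47 |
| 50% | 69.1% | 47.8% | 32.4% | 23.7% | 48 |

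At 25 per arm the fall is from 41% to 25–28%. At d = 0.8 and 30 per arm it is from 86% to 65–68%.

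**Sensitivity to shape.** A 30% cut acts on relative change, so the additive model may not fit. The check simulated 30 per arm with gamma baselines, lognormal proportional change and a 26% relative effect (all assumed). With strongly skewed baselines (shape 1, log-SD 0.4), ANCOVA on the raw score had about 53% power, chi-square on the 30% cut 62%, and ANCOVA on the log score 80%. The last figure agrees with theory: −ln(0.74)/0.4 = 0.75, and 30 per arm has 80% power at d = 0.74. With mild skew (shape 4, log-SD 0.4), raw ANCOVA regains the lead, 69% v 59%.

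**Zero and low baselines.** Percent change = 100 × (follow-up − baseline)/baseline, which is undefined at zero.
- Jaw function: items start at 0 (8.1), but entry requires pain modified by jaw biomechanics, so zero on all 20 items is unlikely.
- Oral behaviours: 21 activities including yawning and gum chewing; zero is implausible.
- GCPS intensity: entry requires diary pain; zero is implausible.
- GCPS disability and HADS: no entry criterion bears on them, so zero or near-zero is plausible, though no frequency is given.
- PPT: a pressure threshold, so a zero baseline is not the concern.

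For illustration, suppose 20% of patients have a zero baseline. Counting them as non-responders turns 40% v 20% into 32% v 16%, and chi-square power at 26 v 25 falls from 35% to 27%. Dropping them (21 v 20) also leaves about 27%.

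**The case against.** The strongest reply is that 12.1 only states hypotheses, while 12.4 sets the tests. Read with 3.2.2, 12.4 already points to a comparison of mean changes, and the Supplemental Materials list a separate Statistical Analysis Plan that might settle the matter. This has weight: a reader might infer that the responder analysis is the fixed plan, and the documents do not support that. But 12.1 presents the proportions as a priori hypotheses to be tested, so the sections still have to agree.

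A second reply is that the power loss depends on the model. This also stands. A reader might infer a fixed, large loss on every scale. The documents give neither responder rates nor distributions, and the skewed simulations show that an untransformed mean comparison can have no advantage. The loss returns once the score is analysed on a suitable scale.

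Third, a reader might infer that percent change fails for all these measures at zero. The entry criteria and the content of the instruments make that unlikely outside GCPS disability and HADS. A reader might also infer that a one-point change from a score of 1 to 3 makes a responder. That needs whole-point sum scores, and the protocol does not say whether totals are sums or means.

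Finally, responder proportions are a legitimate secondary summary in a phase II trial, and changing the analysis does not rescue power. Both are true; they argue for keeping the proportion as support, not for leaving the conflict.

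**Conclusion.** The point holds in a bounded form. The conflict between 12.1 on one side and 3.2.2 and 12.4 on the other is textual and needs no assumption. It covers jaw function, oral behaviours, GCPS, HADS and PPT.

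The cost of following 12.1 is conditional. Under additive normal change it is about 22 percentage points of power at the assumed 40% v 20%, and about 15–18 points at d = 0.5 over control rates of 20–50%, both at 30 per arm. Under strong skew, the advantage of a score analysis depends on choosing the scale in advance.

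The zero-baseline gap is a missing rule that plausibly matters for GCPS disability and HADS. How many patients it would affect cannot be known from the documents. Because these are secondary endpoints, this should be corrected before unblinding but does not threaten the primary comparison.

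**What to change.** In 12.1 and 12.4, make the between-arm difference at Visit 4, adjusted for the baseline score, the analysis of each of the five measures, by ANCOVA or a mixed model. Name the log or rank scale in advance for scores expected to be skewed; a log scale also needs a stated way of handling zeros. State how each total is scored and which visit supplies the baseline. This brings 12.1 and 12.4 into line with 3.2.2.

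Keep the 30% proportion as a descriptive supplement, with a written rule for zero baselines (for example, reported only among patients with a non-zero baseline, with the number excluded shown by arm).

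The cost is wording in two sections and one model per measure, or per site or subscale where these are reported separately. No new data, visits or patients are needed. The downside is that a mean difference is less direct for clinicians, which the retained proportion partly offsets.
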